2.3 BENEFIT–RISK ASSESSMENT

As this is the first-in-human study with RO7565020, no therapeutic benefit is anticipated for participants in Part 1 of this study (as for all early clinical studies in healthy participants) and no long-term benefit to participants with CHB is anticipated in Parts 2 and 3 of this study. However, this study may benefit future patients, as it is essential for the development of new treatments for CHB, and for identifying the appropriate RO7565020 dose for study within a combination therapy setting.

Given no prior clinical experience with RO7565020 exists, the evaluation of the potential risks of treatment and the specific tests, observations, and precautions required for clinical studies with RO7565020 is based primarily on available data from nonclinical toxicology and safety pharmacology studies, as well as information from clinical studies with other anti-HBsAg mAbs. Overall, the level of risk for the individual participants due to treatment with RO7565020 is considered to be minimal and will be managed in a stepwise manner.

The main risk in healthy volunteers is related to the potential development of anti-drug antibody (ADA), while in participants with CHB there is an additional risk associated with target binding and the formation of HBsAg:HBsAb complexes. Risks will be mitigated by conservative selection of the starting dose, careful safety monitoring, staggered dose escalation, sentinel dosing, pre-specified stopping criteria, and well-defined participant characteristics and stopping criteria.

No effect is anticipated from the coronavirus disease 2019 (COVID-19) pandemic on the study benefit–risk assessment or the existing study safety monitoring and risk mitigation measures. Patients with symptomatic disease (including COVID-19) at screening will be excluded and enrolled participants will be closely monitored for new/emerging infections.

More detailed information about the known and expected benefits in the context of potential risks and reasonably expected AEs of RO7565020 is provided in the [IB](#).

3. OBJECTIVES AND ENDPOINTS

The objectives and corresponding endpoints are provided in [Table 5](#).

Table 5 Objectives and Endpoints

| Objectives | Endpoints |
|--|--|
| Primary | |
| 
 • To assess the safety and tolerability: 
 ◦ following a single dose of RO7565020 administered subcutaneously (SC) or intravenously (IV) to healthy participants (Part 1a) and SC to virologically suppressed participants with chronic hepatitis B (CHB) (Part 2) ◦ following multiple doses of RO7565020 administered SC to healthy participants (Part 1b) and virologically suppressed participants with CHB (Part 3) | 
 • Frequency and severity of adverse events (AEs), including adverse events of special interest (AESI), serious adverse events (SAE), and treatment discontinuations due to AEs • Frequency of abnormal laboratory findings based on hematology, blood chemistry (including liver function tests), coagulation and urinalysis test results • Frequency of clinically significant abnormalities in ECGs and vital signs • Mean changes from baseline in vital signs (temperature, systolic and diastolic blood pressure, pulse rate, respiratory rate) over time |
| Secondary | |
| 
 • To investigate the serum pharmacokinetics of RO7565020: 
 ◦ following single-ascending doses of RO7565020 administered SC or IV to healthy participants (Part 1a) and SC to virologically suppressed participants with CHB (Part 2) ◦ following multiple doses of RO7565020 administered SC to healthy participants (Part 1b) and virologically suppressed participants with CHB (Part 3) | 
 • PK parameters of RO7565020: 
 ◦ Time to maximum concentration (t_{max}) ◦ Maximum serum concentration observed (C_{max}) ◦ AUC from Time 0 to time of last sampling point or last quantifiable sample, whichever comes first (AUC_{0-last}) ◦ AUC from Time 0 to infinity (AUC_{inf}) ◦ Terminal half-life ($t_{1/2}$) ◦ Volume of distribution (V_{ss}) and clearance (CL) (IV only) ◦ Apparent clearance (CL/F), apparent volume of distribution at terminal phase (V_z/F) (SC only) |

Table 5 Objectives and Endpoints (cont.)

| Objectives | Endpoints |
|---|---|
| Secondary (cont.) | |
| 
 To characterize the antiviral response after a single dose or multiple doses of RO7565020 in virologically suppressed participants with CHB (Parts 2 and 3, respectively) | 
 Change from baseline in serum quantitative hepatitis B surface antigen (HBsAg) Maximum reduction from baseline of serum HBsAg across all timepoints Proportion of participants with HBsAg loss (on quantitative and qualitative HBsAg assays) Proportion of participants with HBsAg seroconversion (sustained loss of HBsAg and detection of anti-HBs antibody) Proportion of participants with hepatitis B e antigen (HBeAg) loss among HBeAg-positive participants at baseline Proportion of participants with HBeAg seroconversion (sustained loss of HBeAg and detection of anti-HBe antibody) among HBeAg-positive participants at baseline |
| 
 To assess the immunogenicity (induction of anti-drug antibodies [ADAs]) of RO7565020 in healthy participants and virologically suppressed participants with CHB | 
 ADA prevalence at baseline Incidence and titer of ADA over time |
| Exploratory | |
| 
 To characterize the relationship between HBsAg at baseline, the serum concentration of RO7565020 and the maximum reduction of HBsAg (Parts 2 and 3) | 
 Model parameters describing relationships between ratio of RO7565020/HBsAg at baseline and maximum HBsAg reduction |
| 
 To explore the potential impact of ADA on safety and PK/PD after single dose or multiple doses of RO7565020 in healthy participants (Part 1) and virologically suppressed participants with CHB (Parts 2 and 3) | 
 Relationship between ADA, safety, and PK/PD |
| 
 To explore the effect of RO7565020 on other viral biomarkers, such as HBeAg (calculated), HBV RNA, hepatitis B core-related antigen (HBcrAg), total HBsAg after HBsAg:HBsAb complex dissociation, and HBsAg isoforms (Parts 2 and 3) | 
 Baseline and change from baseline in HBeAg (calculated), HBV RNA levels, HBcrAg levels, total HBsAg (after HBsAg:HBsAb complex dissociation), and distribution of HBsAg isoforms |
| 
 To explore the relationship between baseline disease characteristics and efficacy/safety responses (Parts 2 and 3) | 
 Association of the primary and secondary endpoints with the HBV genotype, baseline HBeAg status, and baseline exploratory parameters (such as HBV RNA, HBcrAg, total anti-HBc, HBsAg isoforms) |

Table 5 Objectives and Endpoints (cont.)

| Objectives | Endpoints |
|--|--|
| Exploratory (cont.) | |
| 
 To explore the relationship between HBsAg decrease, HBsAg-HBsAb immune complex formation, and the recovery of the immune response (Parts 2 and 3) | 
 Baseline and change from baseline of cytokines and other soluble markers of immune activation and inflammation Changes in immune cell subsets and activation status (flow cytometry/ICS) and antigen-specific immune response (ELISpot/FluoroSpot) at baseline and post-treatment (PBMC samples) Baseline and changes from baseline in the transcriptional profile of immune cells subsets in peripheral blood (host gene sc-RNAseq) |
| 
 To explore the relationship between potential AEs and inflammatory cytokines released in healthy participants (Part 1) and participants with CHB (Parts 2 and 3) | 
 Association between cytokines and other soluble markers of immune activation and inflammation with AEs |
| 
 To monitor the potential emergence of RO7565020-resistant variants and their impact on efficacy/safety outcomes (Parts 2 and 3) | 
 Baseline and changes in free and total HBsAg over time in relationship to RO7565020 PK Baseline and changes from baseline in binding affinity of RO7565020 to HBsAg Baseline and changes from baseline in the clonality of the S gene sequences |

4. **STUDY DESIGN**

4.1 **OVERALL DESIGN**

An overview of the study design is provided in Section [1.2](#).

This is a FIH, multi-center, dose-finding, and dose-escalation Phase I clinical study of RO7565020 to investigate the safety and tolerability and to characterize the pharmacokinetics, ADA, pharmacodynamics, and preliminary antiviral responses following single and/or multiple doses of RO7565020 in healthy participants and/or virologically suppressed participants with CHB. RO7565020 will be administered via SC injection in healthy participants and participants with CHB, and by IV infusion to healthy participants only. The study will be conducted in three parts: Part 1a is a SAD study in healthy participants with at least 8 participants per cohort. Part 1b is an optional, multiple-dose study with 8 healthy participants in 1 cohort. Part 2 is a SAD study in virologically suppressed participants with CHB with 6 participants in each cohort. Participants will be enrolled into Parts 2a and 2b on the basis of the baseline HBsAg level (cutoff: 3000 IU/mL). Part 3 is an optional, multiple-dose study with 6 virologically suppressed participants with CHB per cohort (see [Figure 1](#)).

A Dose Decision Team (DDT) will review emerging study data and make recommendations regarding dose escalation and overall study conduct (see Section [4.1.1.2](#)). The dose escalation will be stopped according to stopping rules criteria (see Section [4.1.1.3](#)). Additional dose cohorts that assess lower or repeat doses may be investigated; however, dose modifications of the RO7565020 doses of individual participants are not permitted during the study.

Part 1a – SAD in Healthy Participants

Part 1a is a 6:2 randomized, Sponsor-open (i.e., Investigator-blinded, participant-blinded), placebo-controlled SAD study in healthy participants to assess the safety, tolerability, pharmacokinetics, and immunogenicity (in the absence of HBsAg) following SC injection or IV infusion of RO7565020 or placebo. An ethnic-specific cohort is also included for the purpose of PK bridging between a global population and Chinese population.

Four provisional escalating dose levels are planned to be administered sequentially to 6 different cohorts of participants (see [Table 6](#)). The anticipated ascending-dose scheme is 70 mg SC, 230 mg SC, 360 mg SC, 360 mg IV, and 900–1500 mg IV or matching placebo. Cohort 6 (ethnicity bridging cohort: 360 mg SC or matching placebo) may be conducted in parallel with Cohort 4 after the preliminary safety evaluation in Cohort 3 is completed and considered safe.

Each participant within a given cohort will randomly receive single doses of RO7565020 or matching placebo at the assigned dose via SC injection or IV infusion (see [Table 6](#)).

Each cohort will enroll 8 participants to allow for a dose escalating decision. Sentinel dosing will be applied to each cohort, i.e., initially, 2 participants in each cohort will be randomized and dosed (1 with RO7565020 and 1 with placebo). Safety will be evaluated for at least 72 hours after the second sentinel participant has been dosed and if the safety data for the sentinel participants obtained in the 72-hour postdose period are judged acceptable by the Investigator, the remaining participants of the cohort will be dosed.

The study design is adaptive in nature and other intermediate doses may be investigated based on emerging safety and tolerability data. The IV formulation will be used to evaluate the absolute bioavailability of SC formulation, and to provide a higher PK exposure that covers the highest PK exposure (maximum concentration [C_{max}] and area under the time-concentration curve within a dosing interval [AUC_{tau}]) anticipated after multiple doses of SC administration in future Phase II studies.

Part 1b – Multiple Doses in Healthy Participants

Part 1b is an optional, 6:2 randomized, Sponsor-open, placebo-controlled multiple-dose study in healthy participants. If, for example, an unexpected impact on the PK profile due to ADA formation is observed in Part 1a, Part 1b might be initiated to further investigate the safety and pharmacokinetics of RO7565020 following multiple doses.

One dose cohort is planned for Part 1b, and each participant will randomly receive multiple doses of RO7565020 or matching placebo via SC injection. The dose and dosing frequency will be determined by emerging safety and PK data from Part 1a.

In this Part 1b cohort, sentinel dosing will be applied for each dosing to allow an evaluation of safety data for at least 72 hours after the first 2 participants have been dosed (1 with RO7565020 and 1 with placebo). If the safety data for the sentinel participants obtained in the 72-hour postdose period are judged acceptable by the Investigator, the remaining participants will be dosed.

Part 2 – SAD in Participants with CHB

Part 2 is an open-label, SAD study of RO7565020 administered by SC injection in participants with CHB who are virologically (HBV DNA) suppressed with stable NUC treatment, including tenofovir disoproxil fumarate (TDF), tenofovir alafenamide (TAF), or entecavir (ETV). Part 2 aims to assess the safety and tolerability including the potential for HBsAg:HBsAb complex-mediated immune reactions, pharmacokinetics, and pharmacodynamics of RO7565020 in participants with CHB. In addition, proof of mechanism will also be explored by measuring the changes in HBsAg level after treatment. Participants with $20 \text{ IU/mL} \leq \text{HBsAg} \leq 3000 \text{ IU/mL}$ will be enrolled into Part 2a. Participants with $\text{HBsAg} > 3000 \text{ IU/mL}$ will be enrolled into Part 2b (upper limit of 10,000 IU/mL in Cohorts 1 and 2).

Three and four cohorts are planned for Part 2a and Part 2b, respectively. The provisional escalating dose levels are shown in [Table 6](#). Before proceeding to higher dose levels, the safety and tolerability at lower dose levels will be reviewed by the DDT and considered to be safe.

Part 2a Cohort 1 will be initiated after at least 6 participants (5 on active treatment and 1 on placebo) in Part 1a Cohort 2 (i.e., a higher dose level in healthy participants) have completed the 28-day follow-up and the dose level is considered to be safe. The initiation of Part 2b (in participants with $\text{HBsAg} > 3000 \text{ IU/mL}$) will be staggered until at least 5 participants (all on active treatment) at the same dose level in Part 2a ($\text{HBsAg} \leq 3000 \text{ IU/mL}$) have completed at least 28 days of follow-up and the dose level is considered to be safe (see Section [4.1.1](#)). Part 2b Cohort 1 (optional) is designed to assess the target-mediated drug disposition (TMDD) effect on the clearance of anti-HBs mAbs, and the need for this Cohort will be determined after the data from Cohort 1 (Part 2a) are available. If Part 2b Cohort 1 is not needed, Part 2b Cohort 2 will start after at least 5 participants in Part 2a Cohort 2 have completed at least 28 days of follow-up and the dose is considered to be safe. The conduct of Cohort 4 in Part 2b (optional) will be determined by whether a higher dose (720 mg or higher) is required in a high HBsAg population to achieve a meaningful HBsAg reduction and maintenance based on the neutralization potency of RO7565020 in the first 3 cohorts in Part 2b.

Each cohort will enroll 6 participants to allow for a dose-escalation decision. Sentinel dosing of the first participant will be applied to each cohort to allow an evaluation of safety data for at least 72 hours postdose. If the safety data of the sentinel participant obtained in the 72-hour postdose period are judged acceptable by the Investigator, the remaining participants can be dosed.

The HBsAg level of the first 2 participants recruited in Part 2b Cohort 3 and Part 2b Cohort 4 is required to be $\leq 10,000 \text{ IU/mL}$. A participant with $\text{HBsAg} > 10,000 \text{ IU/mL}$ at screening will be on hold until at least 2 participants with $\text{HBsAg} > 3000 \text{ IU/mL}$ but $\leq 10,000 \text{ IU/mL}$ have been dosed and the dose is considered to be safe after 28 days of follow-up.

Part 3 (Optional) – Multiple Doses in Participants with CHB

On the basis of emerging data including safety, tolerability, PK and pharmacodynamic (PD) data from Parts 1 and 2, Part 3 may be initiated as an open-label cohort in participants with virologically suppressed CHB to assess safety, tolerability, pharmacokinetics, pharmacodynamics, and antiviral response after multiple doses of RO7565020 via SC injection, if, e.g., an unexpected PK/PD profile is observed due to ADA formation, or if the dose and dosing interval for the multiple-dose Phase II regimen could not be reliably determined from the single dose PK/PD data.

In Part 3, 6 eligible virologically suppressed participants with CHB are planned to be enrolled in each cohort, for a maximum of 2 cohorts. The dose level and frequency will be determined by the emerging data in Parts 1 and 2. Sentinel dosing will also be applied for each dosing in Part 3 to allow an evaluation of safety data for at least 72 hours after the first participant has been dosed. If the safety data for the sentinel participant obtained in the 72-hour postdose period are judged acceptable by the Investigator, the remaining participants can be dosed.

In Parts 2 and 3, all participants will continue to receive NUC therapy throughout the study, even if HBsAg loss is achieved. Participants should avoid changing NUC during the study including screening period, unless the Investigator considers it necessary for medical reason (e.g., virological breakthrough [Section 8.3.7], safety).

Table 6 Provisional Dose Regimens in Each Study Cohort

| Study part | Study treatment | Background treatment |
|--|---|----------------------|
| Part 1a (healthy participants) | 
 Cohort 1: 70 mg RO7565020 SC (starting dose) or placebo, single dose Cohort 2: 230 mg RO7565020 SC or placebo, single dose Cohort 3: 360 mg RO7565020 SC or placebo, single dose Cohort 4: 360 mg RO7565020 IV or placebo, single dose (over 2-hour infusion) Cohort 5: 900–1500 mg RO7565020 IV or placebo, single dose (over 2-hour infusion) Cohort 6 (PK bridging cohort): 360 mg RO7565020 SC or placebo, single dose | N/A |
| Part 1b (healthy participants) | 
 Multiple doses (3 to 6 doses depending on dosing frequency). Dose level and dosing frequency will be determined using Part 1a data | N/A |
| Part 2a (participants with CHB) | 
 Cohort 1: 70 mg RO7565020 SC (starting dose), single dose Cohort 2: 230 mg RO7565020 SC, single dose Cohort 3: 360 mg RO7565020 SC, single dose | NUC |
| Part 2b (participants with CHB) | 
 Cohort 1 (optional): 70 mg RO7565020 SC, single dose Cohort 2: 230 mg RO7565020 SC, single dose Cohort 3: 360 mg RO7565020 SC, single dose Cohort 4 (optional): 720 mg RO7565020 SC, single dose | NUC |

Table 6 Provisional Dose Regimens in Each Study Cohort (cont.)

| Study part | Study treatment | Background treatment |
|---------------------------------------|---|-----------------------------|
| Part 3 (participants with CHB) | 
Multiple doses (up to 6 doses depending on dosing frequency). Dose level and dosing frequency will be determined using Part 1 and Part 2 data | NUC |

Abbreviations: CHB = chronic hepatitis B; IV = intravenous; N/A = not applicable; NUC = nucleos(t)ide analogue; PD = pharmacodynamic; PK = pharmacokinetic; SC = subcutaneous.

Note: Depending on the evaluation of the safety and/or PK/PD data, the same dose may be repeated; the actual dose may be modified to a lower dose; or intermediate dose-escalation steps other than those anticipated above may be used at the discretion of the Investigator and the Sponsor.

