2.2.3 Background on RO7565020

RO7565020 is a human IgG1 mAb (anti-HBs neutralizing antibody Bc1.187) with a well characterized neonatal Fc receptor (FcRn) affinity-enhancing Fc mutation (M252Y/S254T/T256E; YTE) introduced to increase the half-life and enhance the pharmacokinetic (PK) properties. RO7565020 binds to the antigenic loop present in all forms of HBsAg (L-HBsAg, M-HBsAg, and S-HBsAg) and showed potent and cross-reactive neutralization against genotypes A, B, C, and D in vitro.

Sequential to a single dose of small interfering RNA (siRNA) surrogate, single dose RO7565020 treatment further reduced HBsAg level in the adeno-associated virus (AAV)-HBV mouse model from 3 log₁₀ IU/mL to close to undetectable levels (<0.2 log₁₀ IU/mL).

In addition, RO7565020 can mediate phagocytic cell uptake of HBsAg particles, suggesting that antibody-coated viral particles and/or infected hepatocytes could be eliminated in vivo by phagocytes such as Kupffer cells. The Fc receptor-dependent function of antibody-dependent cellular phagocytosis (ADCP) may also facilitate antigen presentation to antigen-specific T cells, which could stimulate host humoral and cellular immune responses, a phenomenon known as the vaccine-like effect.

A detailed description of the chemistry, pharmacology, nonclinical efficacy and safety of RO7565020 is provided in the [RO7565020 IB](#).

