4.2.2 Rationale for Control Group

In each cohort in Part 1a and in Part 1b, participants will be randomized (Sponsor-open, Investigator-blinded, and participant-blinded) at 6:2 to receive RO7565020 and placebo, respectively. This is considered sufficient to allow for unbiased comparisons of safety and tolerability of active treatment to placebo both within and across cohorts in absence of HBsAg.

It is considered unnecessary to include placebo controls in Parts 2 and 3, because placebo controls have negligible impact on HBsAg change over time, and the off-target safety profile at the same dose will have been assessed in healthy participants and the AEs in the presence of HBsAg would be most likely be of an immunological nature (e.g., as a consequence of HBsAg:HBsAb complex formation and possible tissue deposition) that can be easily attributed.

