4.2.3 Rationale for Biomarker Assessments

4.2.3.1 HBV Dynamic Biomarkers

RO7565020 is a human IgG1 neutralizing antibody, which showed potent and cross-reactive in vitro neutralization against all main circulating viral genotypes of HBsAg. Therefore, the main virological endpoint in this study relies on measuring HBsAg at timepoints defined in the SoA (Section 1.3).

Additional well-established HBV dynamic biomarkers for the assessment of HBV treatment outcomes will include the time course of anti-HBs levels and the evolution of the HBeAg and anti-HBe statuses. In participants who are HBeAg-positive at study entry, a validated research-use-only (RUO) semi-quantitative calculation may be used to follow the time course of serum HBeAg levels over time. In order to evaluate the formation of HBsAg:HBsAb complexes, an assay is being developed by the Sponsor that may be used to either directly quantify the immune complexes or measure HBsAg independently of the putative formation of complexes (i.e., total HBsAg post-dissociation of HBsAg:HBsAb complexes), as appropriate. Additionally, quantification of HBsAg may be measured using a second assay designed to either evaluate a potential bias of the HBsAg quantitative assay being used or to measure a change in the affinity of RO7565020 to escape mutants that might be selected for by therapy with RO7565020.

Several HBV biomarkers have recently emerged in the field that may further support the demonstration of improved virus control. These novel biomarkers will not be used to screen participants and will not have an impact on any clinical decisions or other endpoint evaluation.

Among these, pregenomic HBV RNA, which bypasses reverse transcription and is released in plasma, may provide a direct measure of the transcriptional activity of cccDNA. Consistent with this view, in NUC-treated participants with suppressed HBV DNA, the presence of detectable circulating HBV RNA signals an increased probability of HBV DNA rebound upon NUC cessation ([Wang et al. 2016](#); [Fan et al. 2020](#); [Seto et al. 2021](#); [Kaewdech et al. 2020](#)). In the course of this study, a validated real-time polymerase chain reaction-based investigational assay may be used to quantify HBV RNA.

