4.2.4 Justification for Dose

The starting dose of 70 mg (SAD portions of Part 1 and Part 2) has been selected to balance considerations for an acceptable safety margin and the predicted efficacious dose in humans. RO7565020 was well tolerated at a dose level of 360 mg/kg when administered to cynomolgus monkeys via SC injection or IV once weekly for 3 weeks, thus 360 mg/kg was considered to be a no-observed-adverse-effect level (NOAEL) for both dose routes.

The observed PK exposure (e.g., area under the time-concentration curve from 0 to 21 days [AUC_{0-21d}] and C_{max}) at NOAEL is >100 times higher than the predicted AUC_{inf} and C_{max} values in humans at the proposed starting dose of 70 mg SC, and ~11 and 22 times higher than the predicted AUC_{inf} and C_{max} values, at the planned highest dose of 1.5 g IV in SAD (Part 1a), respectively.

Starting from a single dose of 70 mg in healthy participants also establishes a link to the starting dose in participants with CHB. Based on a PK/PD model, the starting dose of 70 mg in Part 2a is expected to produce a meaningful maximum decline ($\geq 1 \log_{10}$ IU/mL) in free HBsAg concentrations in all participants with baseline HBsAg levels ≤ 3000 IU/mL after a single SC dose of RO7565020.

The planned higher doses (230 mg SC and 360 mg SC) in Part 2a and Part 2b are aiming to achieve greater and more sustained HBsAg reductions in participants with different baseline HBsAg level.

Switching to IV formulation in Part 1a is designed to test a higher dose in healthy participants, which exceeds the maximum SC dose (360 mg) that is feasible with one injection; Part 1a Cohort 5 (900–1500 mg) aims to cover the maximum PK exposure due to PK accumulation after multiple doses. In the meantime, absolute bioavailability of the SC formulation will be evaluated based on the PK data in Cohort 3 and Cohort 4, Part 1a.

Further details are provided in the [RO7565020 IB](#).

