 - Agree to remain abstinent (refrain from heterosexual intercourse) or use of at least one highly effective contraceptive method that results in a failure rate of < 1% per year until 24 weeks after final dose of study treatment. Examples of contraceptive methods with a failure rate of < 1% are in [Appendix 5](#). The Investigator should evaluate with the participant the best contraceptive method based on anatomy and physiology, and lifestyle considerations when possible.
 - Have a negative pregnancy test (blood) within 28 days prior to the first study treatment administration.

b. Biological Male Participants

No contraception measures are needed.

5.2.2 Exclusion Criteria for Parts 2 and 3

Participants are excluded from the study if any of the following criteria apply:

Medical Conditions

1. Pregnant (positive pregnancy test) or lactating women
2. Anti-HBs antibody positive at screening
3. Current co-infection with other pathogens such as HAV, HCV, *hepatitis D virus* (HDV), *hepatitis E virus* (HEV), or HIV
4. Evidence of liver cirrhosis or decompensated liver disease such as ascites, esophageal or gastric varices, splenomegaly, nodular liver, jaundice, hepatic encephalopathy, or portal hypertension
5. History of or suspicion of HCC (e.g., elevated α -fetoprotein [AFP] levels, or suggestive lesions on abdominal ultrasound or other imaging)
6. History or other evidence of a medical condition associated with chronic liver disease other than HBV infection (e.g., hemochromatosis, autoimmune hepatitis, alcoholic liver disease, toxin exposure, thalassemia, nonalcoholic steatohepatitis, metabolic liver disease)
7. Expected to need systemic antiviral therapy other than that provided by the study at any time during their participation in the study, with the exception of oral/ topical therapy for HSV I or HSV II
8. History of immunologically mediated disease (e.g., inflammatory bowel disease, idiopathic thrombocytopenic purpura, lupus erythematosus, autoimmune hemolytic anemia, scleroderma, severe psoriasis, rheumatoid arthritis, multiple sclerosis, or any other autoimmune disease)
9. History of clinically significant and not adequately controlled cardiovascular, endocrine, gastrointestinal, renal, ocular, pulmonary, or neurological disease
10. History of clinically significant psychiatric disease
11. Evidence of an active or suspected cancer or a history of malignancy other than adequately treated basal cell carcinoma

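### HBsAg seroconversion sets no condition on antibody source, so if the anti-HBs assay reads RO7565020, itself an anti-HBs antibody, a case counted during exposure could be drug alone

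*Combined protocol and SAP*

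**What the plan says.** **Endpoint.** Section 3, Table 5 (and the synopsis) gives, for Parts 2 and 3: "Proportion of participants with HBsAg seroconversion (sustained loss of HBsAg and detection of anti-HBs antibody". Section 9.4.5, Table 12 tabulates HBsAg loss and seroconversion as proportions of the PD analysis set at each timepoint. Neither place sets a condition on antibody source, anti-HBs titre or drug concentration, or says how many visits make a loss sustained.

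**Drug.** Section 2.2.3 states "RO7565020 is a human IgG1 mAb (anti-HBs neutralizing antibody Bc1.187" and describes an Fc mutation "introduced to increase the half-life and enhance the pharmacokinetic (PK) properties". Section 8.6 describes the drug in the same terms. Section 4.1 (Part 2) says optional Part 2b Cohort 1 is "designed to assess the target-mediated drug disposition (TMDD) effect on the clearance of anti-HBs mAbs".

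**Expected effect.** Section 4.2.4 expects the 70 mg starting dose in Part 2a to give a maximum decline of at least 1 log10 "in free HBsAg concentrations in all participants with baseline HBsAg levels" up to 3000 IU/mL.

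**Baseline.** Section 5.2.2 lists as an exclusion: "Anti-HBs antibody positive at screening".

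**Assays.** Section 8.7.1 describes the anti-HBs test only as quantitative, and Section 4.2.3.1 plans to follow its time course. For HBsAg, the same section adds that "quantification of HBsAg may be measured using a second assay designed to either evaluate a potential bias of the HBsAg quantitative assay being used". Section 8.5 measures both total and active RO7565020.

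**The concern.** The drug belongs to the class of antibody that the endpoint counts, and it is also meant to bring down the antigen whose loss is the other half of the definition. One administered product could therefore contribute to both conditions. Because anti-HBs positives are excluded at screening, anti-HBs found after dosing would be new host antibody, drug (if the assay reads it), or both. The plan has no rule for telling these apart when the endpoint is scored.

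The stake is interpretation. Section 2.2.3 puts forward a vaccine-like effect, in which treatment could stimulate host humoral and cellular immunity. Drug scored as seroconversion would look like evidence for that effect. No hypothesis test, stopping rule or primary result depends on the endpoint (Sections 4.1.1.3 and 9.1).

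**Working it through.** The plan gives no expected rate of HBsAg loss or seroconversion, so there is no figure of its own to reproduce on this point. The check is mainly a reading of the passages, with arithmetic for scale.

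**1. When drug alone would be counted.** Two things must hold in the same participant: sustained HBsAg loss, and anti-HBs detected. The second can come from drug only if the assay reads RO7565020, which no section states. The first is not implied by Section 4.2.4: a 1 log10 fall from the lowest eligible Part 2a baseline (20 IU/mL, Section 5.2.1) leaves 20/10 = 2 IU/mL, which is a fall and not necessarily a loss. The count may therefore be zero.

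**2. Whether another provision covers it.** The second assay in Section 4.2.3.1, and the free-versus-total comparisons in Sections 4.2.3.3 and 8.7.3, concern HBsAg. Sections 9.4.6 and 9.4.7 allow PK/PD modelling and biomarker summaries against PK, but these are optional or exploratory and leave the Table 12 rule as it is.

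**3. Size per case.** One case in a cohort of 6: 1/6 = 16.7 points (exact 95% CI for 1 of 6: 0.4% to 64.1%). Over all planned CHB participants (30 to 54, Section 9.2): 1/30 = 3.3 points to 1/54 = 1.9 points.

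**4. Could drug still be present when the endpoint is tabulated?** The documents give no half-life, so the values below are assumptions. They use single-exponential decline from dosing, ignoring SC absorption. Target-mediated disposition, which may shorten exposure in CHB, enters only through the shorter half-lives. Fraction remaining = 2^(-t/half-life), with t = 84 days at Day 85 and 168 days at Day 169. The last two columns give the first Part 2 visit (Days 29, 57, 85, 113, 141, 169, then 225, 281, 337, 393 if follow-up is extended) at which drug is below an assumed assay limit of 1% or 0.1% of peak. Those levels are reached after 6.64 and 9.97 half-lives.

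| Assumed half-life (days) | Left at Day 85 | Left at Day 169 | First visit below 1% | First visit below 0.1% |
|---|---|---|---|---|
| 10 | 0.3% | <0.001% | Day 85 | Day 113 |
| 20 | 5.4% | 0.3% | Day 141 | Day 225 |
| 30 | 14.4% | 2.1% | Day 225 | Day 337 |
| 45 | 27.4% | 7.5% | Day 337 | none by Day 393 |
| 60 | 37.9% | 14.4% | none by Day 393 | none by Day 393 |

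Example: 6.64 × 30 = 199 days, and the first visit at least that late is Day 225 (224 days). Across this range, drug could overlap with many of the tabulated visits. Whether it would read positive depends on the assay.

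**5. 'Sustained'.** Part 2 samples HBsAg and serology on Days 2, 3 and 4, which are 24 hours apart. With no stated duration, a short loss soon after dosing is not clearly ruled out.

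**The case against.** **The plan is not blind to drug interference.** Anti-HBs is quantitative and followed over time, PK is sampled at the same Part 2 visits, and HBV-specific cellular responses are explored. Anti-HBs that falls with the drug can be told from anti-HBs that rises or persists as drug declines. This stands as a resource, and the fix uses it. It does not change how Table 12 scores a case.

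**A concentration cut-off could empty the endpoint.** At longer half-lives no visit would be attributable, and a true host response during exposure could not be labelled seroconversion. This stands. A cut-off alone would discard the anti-HBs time course, so it needs a case listing beside it.

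**The impact is small.** The endpoint is descriptive, Section 2.3 anticipates no long-term benefit in Parts 2 and 3, and any case in a cohort of 6 could be reviewed individually. This also stands, and it limits the weight of the point. It does not supply the missing rule.

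**A reader might infer that the lack of a placebo group is part of the problem.** Section 4.2.2 says: "It is considered unnecessary to include placebo controls in Parts 2 and 3, because placebo controls have negligible impact on HBsAg change over time". Anti-HBs is not mentioned there. But the ambiguity is between drug and host antibody induced by treatment. Both would be absent on placebo, so a placebo group could not separate them. This is an assay and labelling question, not a design defect.

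**Conclusion.** The point holds in conditional form. As written, Tables 5 and 12 count any detected anti-HBs together with HBsAg loss as seroconversion. If the anti-HBs assay detects RO7565020, a participant with HBsAg loss during exposure could be counted on drug alone. Each such case is worth 16.7 points in a cohort of 6.

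A reader might go further and conclude that reported seroconversion will be inflated. The documents do not support that. They are silent on whether the assay reads the drug, they give no expected rate of HBsAg loss, and the number affected could be zero. If the assay does not detect the drug, the source question closes. The persistence figures rest on assumed half-lives and assay limits and show only that overlap is plausible.

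The rule is worth settling before results are seen, because a workable one can be built largely from data already scheduled.

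**What to change.** 1. State whether the anti-HBs assay detects RO7565020 and, if so, the lowest concentration that reads positive, naming total or active drug. If it does not detect the drug, leave the antibody part of the endpoint unchanged.
2. If it does, or if this is unknown, split the Table 12 seroconversion row by the RO7565020 concentration at the same visit. Use *seroconversion* where drug is below the concentration that reads positive, or below PK quantification provided that limit is no higher. Report the rest as *HBsAg loss with anti-HBs not distinguishable from drug*. While the assay's limit is unknown, no visit can be shown to meet the first label.
3. For every case, list quantitative anti-HBs beside RO7565020 concentration over time, so that anti-HBs rising or persisting as drug falls is visible.
4. Define 'sustained' as a number of consecutive visits with a stated minimum interval, so that Days 2 to 4 cannot qualify. The two-consecutive-visit form in Table 3, note a, belongs to follow-up visits 56 days apart and does not carry over without an interval. From Day 29 to Day 169, Part 2 visits are 28 days apart, so an interval of that length needs no extra visit.

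**Cost.** One assay statement, revised endpoint wording, one split row and one listing. Part 2 needs no new samples, since serology and PK share visits, and a participant whose HBsAg has not returned by Day 169 has up to four further visits. In Part 3, serology may be thinned (Table 4, note o), so some pairs may be missing and the split applies only where both results exist. The main downside is that many visits, possibly all, may fall in the *not distinguishable* row.
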